### Assessment of Causality

The relationship between the occurrence of an AE and the IMP will be assessed using the categories presented below. For expedited reporting and all other purposes, the categories “none” and “unlikely” will represent no evidence or argument to suggest a causal relationship, while “possible”, “probable” and “definite” will be seen to convey that there is evidence or argument to suggest a causal relationship. Following worst case scenario all AEs without a causality assessment from the investigator will be classified as “possible”.

---

None	The time interval between the administration of the IMP and the occurrence or worsening of the AE rules out a relationship, and/or  another cause is established and there is no evidence of a (concomitant) causal connection with or worsening caused by the IMP.
Unlikely	The time interval between administration of the IMP and the occurrence or worsening of the AE makes a causal relationship unlikely, and/or  the known effects of the IMP or substance class provide no indication of a (concomitant) causal connection with or worsening caused by the IMP and there is another cause which serves as an adequate explanation, and/or  although the known effects of the IMP or substance class make it possible to derive a plausible causal chain with regard to a (concomitant) causal connection or worsening, however, another cause is considerably more likely, and/or  another cause of the AE has been identified and a (concomitant) causal connection with or worsening caused by the IMP is unlikely.

---

---

Possible	
A plausible causal chain with regard to a (concomitant) causal connection with / worsening of the AE can be derived from the pharmacological properties of the IMP or substance class. However, other approximately equally likely causes are known, or
 
although the pharmacological properties of the IMP or substance class provide no indication of a (concomitant) causal connection with / worsening of the AE, there is no other known cause which provides an adequate explanation.

Probable	
The pharmacological properties of the trial medication or substance class, and/or
 
the course of the AE after discontinuation of the IMP and possible subsequent re-exposure, and/or
 
specific findings (e.g. positive allergy test or antibodies against the IMP / metabolites ) suggest a (concomitant) causal connection with / worsening of the AE resulting from the IMP, however another cause cannot completely be ruled out.

Definite	
The pharmacological properties of the IMP or substance class and/or
 
the course of the AE after discontinuation of the IMP and possible subsequent re-exposure, and/or
 
specific findings (e.g. positive allergy test or antibodies against the IMP / metabolites ) definitely indicate that there is a (concomitant) causal connection with / worsening of the AE resulting from the IMP and there are no indications of other causes.

---

### 8.2.6 Solicited AEs

After each vaccination subjects receive a memory aid to record solicited local and general AEs most likely to occur on the day of vaccination and the following seven days (Days 0-7; 8-day period).

All solicited symptoms observed after vaccination with details concerning the intensity and the course of the reaction should be documented there. The investigator will collect this information during the following scheduled visits and transfer it to the eCRF and the subject's medical record. Local and general reactions still ongoing after seven days will be measured or examined each day until resolution or until no further change can reasonably be expected, and the last day of symptoms and maximum intensity will be documented in the memory aid.

In case of severe and unexpected local and/or general reactions, the subject should be instructed to contact the trial physician outside of scheduled trial visits.

### 8.2.6.1 Solicited Local AEs

The solicited local symptoms erythema, swelling, induration, pruritus and pain at the injection site are to be documented in the memory aid by the subject.

To standardize procedures, uniform rulers will be handed out to all subjects for measurements of erythema, swelling and induration diameters, as will digital thermometers for oral measurements of body temperature.

#### Assessment of Intensity

Injection site erythema	size measured in diameter
Injection site swelling	size measured in diameter
Injection site induration	size measured in diameter

The maximum severity will be scored as follows:

0	=	0
1	=	< 30 mm
2	=	≥ 30 – <100 mm
3	=	≥ 100 mm

Injection site pruritus:

0	=	Absent
1	=	Mild
2	=	Moderate
3	=	Severe

Injection site pain:

0	=	Absent
1	=	Painful on touch
2	=	Painful when limb is moved
3	=	Spontaneously painful / prevents normal activity

#### Assessment of Causality

Solicited local AEs are defined as being related to the vaccine.

### 8.2.6.2 Solicited General AEs

The solicited general symptoms body temperature, headache, myalgia, nausea, chills and fatigue are to be documented in the memory aid by the subject.

#### Assessment of Intensity

Subjects are asked to document the solicited general AEs in the memory aid as described in [Table 5](#) below. In the subject’s memory aid, the grading of maximum symptom intensity is described in basic, easily understood language based on the following descriptions:

**Table 5 Grading of General Symptoms from the Subject’s Memory Aid**

MedDRA coded Preferred Term General AEs	Grade	Maximum Severity
Body temperature*	0	< 99.5°F (< 37.5°C)
	1	≥ 99.5 – <100.4°F (≥ 37.5 – < 38.0°C)
	2	≥ 100.4 – <102.2°F (≥ 38.0 – < 39.0°C)
	3	≥ 102.2 – <104.0°F (≥ 39.0 – < 40.0°C)
	4	≥ 104.0°F (≥ 40.0°C)
Headache, Myalgia, Nausea, Chills and Fatigue	0	None
	1	Mild: easily tolerated, minimal discomfort and no interference with daily activity
	2	Moderate: Some interference with daily activity
	3	Severe: Prevents daily activity

\*Pyrexia is defined as oral temperature ≥ 100.4°F (≥38.0°C).

### Assessment of Causality

Causal relationship between solicited general AEs and the vaccine will be assessed by the investigator using the same categories as for unsolicited AEs (see [Section 8.2.5](#)).

### **8.2.7 Cardiac Assessment**

To evaluate the cardiac profile of MVA-BN®, targeted physical exams including auscultation of the heart and lung will be performed ([Section 8.2.3](#)). Any kind of cardiac signs (i.e. discovered by the physician during examination of the patient) or symptom(s) (i.e. experienced and reported by the subject) detected during the trial such as but not limited to chest pain, dyspnea, arrhythmia or edema are recorded.

### ECG

A standard 12-lead ECG will be taken at the SCR and at Visit 2. At Visit 4 and Visit 7 (Group 3 only) an ECG is only done if clinically indicated. ECGs will be evaluated by a central ECG reading center. The workflow and communication flow will be provided in a separate manual.

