## 1.6 Trial Procedure Schedule

Visit (V)	SCR	V1	V2	V3	V4	V5	V6*	V7*	V8*	FU 1	FU 2
Day / Visit +... Day	-28--1	0	V1+ 12-16	V1+ 28-35	V3+ 12-16	V3+ 28-35	V1+ 84-96	V6+ 12-16	V6+ 28-35	V3 (V6*)+ 182-210	V3 (V6*)+ 364-392
Target week	- 4	0	2	4	6	8	12	14	16	30 (38*)	56 (64*)
Procedures											
Informed consent & HIPAA	X										X 
Check incl. / excl. criteria	X	X									
Medical History/HIV specific medical history	X										
Check criteria for withdrawal of next vaccination				X			X				
Assessment for previous smallpox vaccination including check for a scar	X										
Complete physical exam	X										
Evaluation of vital signs	X	X	X	X	X	X	X	X	X	X	X
Calculate individual cardiac risk factor	X										
Evaluation of family cardiac risk factors	X										
Targeted physical exam incl. auscultation of the heart and lung		X	X	X	X	X	X	X	X	X	X
ECG 	X		X		(X) 			(X) 			
Recording of prior and concomitant medication	X	X	X	X	X	X	X	X	X		
Counseling on avoidance of pregnancy for WOCBP 	X	X		X			X				
AE/SAE/AESI recording	X	X	X	X	X	X	X	X	X	X 	X 
Lab											
Pregnancy test for WOCBP 	X	X		X		X	X		X		
Obtaining blood for safety lab 	X		X		X			X		(X) 	(X) 

Visit (V)	SCR	V1	V2	V3	V4	V5	V6*	V7*	V8*	FU 1	FU 2
Day / Visit +... Day	-28--1	0	V1+ 12-16	V1+ 28-35	V3+ 12-16	V3+ 28-35	V1+ 84-96	V6+ 12-16	V6+ 28-35	V3 (V6*)+ 182-210	V3 (V6*)+ 364-392
Target week	- 4	0	2	4	6	8	12	14	16	30 (38*)	56 (64*)
Total, HDL and LDL cholesterol	X										
Troponin I testing 	X		X		X			X			
Serum collection for immunogenicity testing		X		X	X		X	X		X	X
CD4 count	X		X		X			X	X	X	X
Viral Load 	X		X								
Vaccination											
Vaccine administration & Subject observation		X		X			X				
Recording of immediate AEs		X		X			X				
Handout of memory aid		X		X			X				
Collection of memory aid			X		X			X			
Examination of injection site			X		X			X			
Blood volume											
Appr. blood volume drawn (ml) 	13	9	13	9	18	0	9	18	2	11	11
Cumulative blood volume drawn (ml) 	13	22	35	44	62	62	71	89	91	102	113

\*Visits performed for subjects in Group 3 only

(x) Only to be performed if clinically indicated, i.e. in the presence of cardiac signs or symptoms.

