### **8.1.2.3 AESIs**

An AESI is defined in this trial as:

- Any cardiac sign or symptom developed since the first vaccination
- ECG changes determined to be clinically significant
- Cardiac enzyme troponin I  $\geq 2 \times$  ULN

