### Troponin I

Troponin I will be measured at SCR and on the following visits: Visit 2, Visit 4 and Visit 7 (Group 3 only).

Cardiac events fulfill the definition of an AESI as described in [Section 8.1.2.3](#). The investigator will be asked to assess the clinical significance of the case.

Case definitions as published by the CDC ([Morbidity and Mortality Weekly Report \[MMWR\] May 30, 2003](#)) are provided in [Section 16.2](#); [Appendix II: Case Definitions Acute Myocarditis / Pericarditis](#) in order to:

[figure not shown]
- help investigators to recognize possible events of acute myocarditis and/or pericarditis and
- distinguish from unspecific and isolated ECG changes without or with unclear clinical significance.

Subjects who develop any kind of cardiac signs or symptoms during the trial such as but not limited to chest pain, dyspnea, arrhythmia or edema are referred to a local cardiologist for cardiac evaluation such as (treadmill) ECG, measurement of cardiac enzyme and/or echocardiogram. Depending on the results of these evaluations, further diagnostic tests will be done as recommended by the cardiologist and subjects will be followed up at a frequency determined by the cardiologist. Any AESIs occurring after at least one vaccination will be followed up until complete resolution or until the sequelae are stable and considered to be permanent.

In any case of cardiac signs or symptoms, or increased laboratory results for Troponin I, the subject will be asked to attend for an unscheduled visit at the site, in order to perform or repeat Troponin I testing, to perform a physical examination for cardiac symptoms and to record an unscheduled ECG.

Further details regarding the follow-up of AESIs are described in the ‘Investigator’s Manual – Follow-up of Adverse Events of Special Interest’.

[Figure 1](#) outlines the algorithm for assessment of cardiac events.

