#### HIV Related

- Viral Load (only at Visit SCR and Visit 2)
- CD4 count (at Visit SCR, Visit 2, Visit 4, Visit 7, Visit 8 and FU 1 and FU 2)

Pregnancy test (serum  $\beta$ -HCG pregnancy test at SCR and urine  $\beta$ -HCG pregnancy test within 24 hours prior to each vaccination and at last active trial phase visit for women of childbearing potential).

Information on all pregnancy tests will be listed.

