#### Serious Adverse Events

The number of subjects with at least one SAE during the trial will be descriptively compared between the treatment groups, and between vaccination periods within Group 3.

SAEs reported will be listed in the same manner as for AEs.

The number of subjects with at least one Treatment Emergent SAEs will be descriptively compared between the treatment groups, and between vaccination periods within Group 3.

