#### Adverse Events of Special Interest

AESIs will be reported separately but in the same way as SAEs.

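### The only routine post-vaccination ECG follows the first vaccination, so the AESI comparison between vaccination periods in Group 3 can favour the later vaccinations if silent ECG changes occur

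*Protocol*

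**What the plan says.** Protocol Section 8.1.2.3 gives three separate AESI criteria: a cardiac sign or symptom, troponin I of at least twice the upper limit of normal (ULN), and "ECG changes determined to be clinically significant".

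The ECG part of Protocol Section 8.2.7 sets the routine recordings: "A standard 12-lead ECG will be taken at the SCR and at Visit 2". For later vaccinations it says: "At Visit 4 and Visit 7 (Group 3 only) an ECG is only done if clinically indicated". A footnote to the schedule in Section 1.6 explains the condition: "Only to be performed if clinically indicated, i.e. in the presence of cardiac signs or symptoms". The troponin part of Section 8.2.7 adds a second trigger. An unscheduled visit with an ECG follows "In any case of cardiac signs or symptoms, or increased laboratory results for Troponin I".

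In SAP Section 3.5.9, subjects with at least one SAE are compared descriptively between groups and "between vaccination periods within Group 3". The next paragraph carries this over: "AESIs will be reported separately but in the same way as SAEs". Table 15.3.2.2 tabulates AESI incidence per vaccination period. The SAP does not mention that the ECG criterion is assessed differently across periods.

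**The concern.** A comparison between periods is fair only if an event of a given kind has the same chance of being found in each. For one AESI criterion this fails. Visit 2 falls 12 to 16 days after vaccination 1, inside the 28-day period 1, and every subject has an ECG there whether or not anything is wrong. After vaccination 2 and the booster, something else must first raise suspicion.

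The difference runs in the reassuring direction. The trial asks whether more doses or injections remain safe, and the within-Group-3 period comparison is a natural place to look for a booster signal. AESI counts will probably be small, so one event found only by the Visit 2 ECG could create an apparent decline.

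Two features add to this. Under the SAP's general definitions, an AESI that is also serious moves to the SAE analysis. The AESI table therefore holds the non-serious ones, where silent ECG findings would mostly sit. Protocol Section 4.2.5 lists an AESI among the criteria for no further vaccination, so subjects with a period-1 AESI can drop out of the later periods.

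**Working it through.** **The plan's own safety figure.** Protocol Section 9.2 claims at least 95% probability of seeing an event of incidence 1 in 10 with 30 subjects: 1 − 0.9^30 = 0.958. This reproduces. The documents give no figure for AESI detection.

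**Detection routes by period** (Protocol Sections 1.6, 8.2.3 and 8.2.7)

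| AESI criterion | Period 1 | Period 2 | Period 3 (Group 3) |
|---|---|---|---|
| Sign or symptom | Examination at every visit | Same | Same |
| Troponin | Visit 2 | Visit 4 | Visit 7 |
| Significant ECG change | Routine at Visit 2, plus any triggered ECG | Triggered ECG only | Triggered ECG only |

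Only the last row is unequal, and only for changes with no sign, no symptom and normal troponin.

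**Model.** Let true risk be the same in every period, with 30 subjects at risk in each.
- q: risk per period of a silent significant ECG change that only a routine ECG would find (assumed).
- r: risk per period of an AESI found by sign, symptom, troponin or a triggered ECG (assumed; 3% below).

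Observed risk is 1 − (1 − r)(1 − q) in period 1 and r in periods 2 and 3. Expected extra period-1 AESIs are 30q. The probability of at least one is 1 − (1 − q)^30.

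| q | Extra AESIs in period 1 | P(at least one) | Observed period-1 risk, r = 3% | Apparent risk ratio, later period vs period 1 |
|---|---|---|---|---|
| 0 | 0 | 0 | 3.0% | 1.00 |
| 1% | 0.3 | 26% | 1 − 0.97 × 0.99 = 3.97% | 0.76 |
| 2% | 0.6 | 45% | 1 − 0.97 × 0.98 = 4.94% | 0.61 |
| 5% | 1.5 | 79% | 1 − 0.97 × 0.95 = 7.85% | 0.38 |

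The true ratio is 1.00 in every row. At r = 3%, the chance that period 1 shows more AESIs than period 2 is 43% at q = 1%, against 28% for the reverse. At q = 5% it is 71% against 12%.

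**Sensitivity to r.** For r from 1% to 9.9%, the apparent ratio runs from 0.50 to 0.92 at q = 1%, and from 0.17 to 0.69 at q = 5%.

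**If the booster really raised r by half, to 4.5%.** The planned comparison would show 4.5/3.97 = 1.13, 4.5/4.94 = 0.91 and 4.5/7.85 = 0.57 at q = 1%, 2% and 5%. A comparison limited to AESIs detectable in every period would show 4.5/3.0 = 1.50 whatever q is.

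**After the fix, with equal true risk.** Observed risk is r in every period and the ratio is 1.00. The model ignores the loss of subjects under Section 4.2.5.

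**The case against.** Several counter-arguments are good.

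- **The gap is narrow.** A reader might infer from the Section 1.6 footnote that no symptom-free subject can have an ECG-based AESI after vaccination 2 or the booster. Section 8.2.7 does not support that. An increased troponin also triggers an ECG, this trigger is not tied to the 2 × ULN criterion, and auscultation at each visit can reveal a sign. This stands, and it limits the problem to changes with no sign, no symptom and normal troponin.
- **The rate is unknown and may be low.** Inclusion criterion 17 and the cardiac exclusions remove subjects with significant findings at entry. Section 8.2.7 also helps investigators set aside isolated ECG changes of unclear significance. At q = 1% there is a 74% chance of no such event among 30 subjects. This stands.
- **The comparison between groups is unaffected.** All three groups have the same routine ECGs, so the schedule does not bias the regimen comparison. This stands. The affected comparison lies within one arm and is descriptive, so no error rate or power is at issue.
- **Viral load is a different matter.** It too is scheduled only at screening and Visit 2, and a reader might extend the point to it. It is not an AESI criterion, and no comparison of it between periods is planned.
- **The ECG tables are already clear.** SAP Section 3.5.11 confines the ECG summary and shift table to screening and Visit 2, so relabelling would add little.
- **The listings allow case-by-case review.** Planned listings cover AESIs, their cardiac follow-up and all ECGs. That helps a careful reader, but it does not correct Table 15.3.2.2 or the comparison drawn from it.

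**Conclusion.** The concern holds in a limited form. Followed as written, the SAP compares AESIs between Group 3 vaccination periods with unequal ascertainment for one of three criteria, and the inequality can only favour periods 2 and 3. The size depends on an assumed rate: 0.3 to 1.5 extra expected period-1 AESIs per 30 subjects for q of 1% to 5%, and none if silent changes do not occur.

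A reader might conclude that the plan necessarily makes the booster look safer, or that a fall in AESIs is to be expected even if risk rises. The documents do not support either. The effect needs q above zero, and at r = 3% and q = 1% a rise in later-period risk from 3% to 4% would already offset it (period-1 observed risk is 3.97%). Nor does the point undermine the between-group safety assessment. It calls for an inexpensive improvement to one descriptive comparison.

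**What to change.** In SAP Section 3.5.9 and Table 15.3.2.2:

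1. Classify each AESI by detection route (sign or symptom, troponin, ECG triggered by either, routine Visit 2 ECG only) from the ECG, troponin and AE data already collected. Section 8.2.7 speaks only of increased troponin, so state the level taken to count as a trigger. Give AESIs of unclear route their own row.
2. Base the within-Group-3 period comparison on AESIs detectable in every period, leaving out those found only by the routine Visit 2 ECG.
3. Show the all-AESI count beside it, so that nothing is hidden.
4. State that the denominator in each period is the subjects who received that vaccination. Note that an AESI is a criterion for no further vaccination, so later periods hold a selected subset. The restricted comparison does not remove that selection.

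The cost is a few sentences and one derived variable. The downside is fewer AESIs in the period comparison. The ECG schedule need not change, and whether to add ECGs is a clinical decision outside this point.

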### Cardiac Risk Factors

The individual cardiac risk factor is calculated at SCR (for subjects 20 years of age and older), using the National Cholesterol Education Program’s risk assessment tool

---

(<http://hin.nhlbi.nih.gov/atp/iii/calculator.asp?usertype=prof>). Subjects with a 10% or greater risk of developing a myocardial infarction or coronary death within the next 10 years are excluded from trial participation.

In addition, the family cardiac risk factor is evaluated at SCR. Subjects with an immediate family member (father, mother, brother, or sister), who has had onset of ischemic heart diseases before 50 years of age, are also excluded from trial participation.

### Troponin I

Troponin I will be measured at SCR and on the following visits: Visit 2, Visit 4 and Visit 7 (Group 3 only).

Cardiac events fulfill the definition of an AESI as described in [Section 8.1.2.3](#). The investigator will be asked to assess the clinical significance of the case.

Case definitions as published by the CDC ([Morbidity and Mortality Weekly Report \[MMWR\] May 30, 2003](#)) are provided in [Section 16.2](#); [Appendix II: Case Definitions Acute Myocarditis / Pericarditis](#) in order to:

[figure not shown]
- help investigators to recognize possible events of acute myocarditis and/or pericarditis and
- distinguish from unspecific and isolated ECG changes without or with unclear clinical significance.

Subjects who develop any kind of cardiac signs or symptoms during the trial such as but not limited to chest pain, dyspnea, arrhythmia or edema are referred to a local cardiologist for cardiac evaluation such as (treadmill) ECG, measurement of cardiac enzyme and/or echocardiogram. Depending on the results of these evaluations, further diagnostic tests will be done as recommended by the cardiologist and subjects will be followed up at a frequency determined by the cardiologist. Any AESIs occurring after at least one vaccination will be followed up until complete resolution or until the sequelae are stable and considered to be permanent.

In any case of cardiac signs or symptoms, or increased laboratory results for Troponin I, the subject will be asked to attend for an unscheduled visit at the site, in order to perform or repeat Troponin I testing, to perform a physical examination for cardiac symptoms and to record an unscheduled ECG.

Further details regarding the follow-up of AESIs are described in the ‘Investigator’s Manual – Follow-up of Adverse Events of Special Interest’.

[Figure 1](#) outlines the algorithm for assessment of cardiac events.

**Figure 1 Algorithm for Assessment of Cardiac Events**

\*At any protocol-scheduled ECG and/or troponin I abnormality, the algorithm will begin at this point.

## 8.2.8 Safety Laboratory Measurements

The intensity of laboratory / systemic quantitatively measured toxicities will be graded according to the toxicity scale in [Section 16.1; Appendix I: Toxicity Scale for Laboratory Values](#). These grading scales include the laboratory values determined with the routine safety parameters. In case of other laboratory values not included in the routine safety laboratory and not listed in [Section 16.1; Appendix I: Toxicity Scale for Laboratory Values](#), the [Division of AIDS Table for Grading the Severity of Adult and Pediatric Adverse Events, Version 1.0](#), December 2004, Clarification August 2009 will be used for grading of laboratory toxicities.

Safety laboratory is determined at SCR, Visit 2, Visit 4, Visit 7 (Group 3 only) and at any other visit(s) if clinically indicated. The safety laboratory measurements are performed at a central laboratory. Laboratory normal ranges are provided by the central laboratory and filed in the Investigator File. Safety laboratory parameters to be evaluated are:

Hematology: Red blood cell count, hemoglobin, total and differential White Blood Cell count (WBC), platelet count (Hematocrit, mean corpuscular/cell volume (MCV), mean corpuscular/cellular hemoglobin (MCH) , mean corpuscular hemoglobin concentration (MCHC) and red blood cell distribution width (RDW) are routinely performed as part of the complete blood cell count and will be included in the laboratory report).

HIV specific parameters: CD4 count will be determined with every safety laboratory and at Visit 8 and FU 1 and FU 2. Viral load will be determined at SCR and at Visit 2. Viral load will be determined at any other visit if clinically indicated.

Serum chemistry:

Total bilirubin, AP, AST, ALT, serum creatinine (for calculation of CrCl at SCR), sodium, potassium, calcium, troponin I (troponin mandatory at SCR and in addition Visit 2, Visit 4 and Visit 7 (Group 3 only)).

Pregnancy test:

A  $\beta$ -human choriongonadotropin (HCG) pregnancy test will be conducted for all WOCBP at SCR, within 24 hours prior to each vaccination and at the individual last active trial phase visit (i.e. Visits 1, 3, 5 and Visits 6 and 8 for Group 3 respectively). At SCR a serum  $\beta$ -HCG pregnancy test will be performed; all other pregnancy tests will be conducted as urine  $\beta$ -HCG tests.

The following parameters will only be evaluated during the screening period for assessment of inclusion / exclusion criteria and at the following visits only if clinically indicated:

Cholesterol  
Total, HDL and LDL

---

